6.1.3. Ibrutinib Hold After Withdrawal of All Immunosuppressants

At the physician's discretion, ibrutinib may be held if all of the following conditions are met:

- All systemic immunosuppressants used for the treatment of cGVHD have been discontinued.
- cGVHD response has been maintained for 12 weeks after complete withdrawal of all immunosuppressants (not including ibrutinib).
- The subject has received a minimum of 48 weeks of ibrutinib.

If cGVHD returns/worsens after ibrutinib has been held for the above criteria, ibrutinib may be restarted after consulting with the medical monitor.

7. INTERVENTION COMPLIANCE

The first dose of ibrutinib will be delivered at the study site on Week 1 Day 1, after which subsequent dosing will occur on an outpatient basis. Intervention compliance will be assessed based on clinical interview with subjects at each study visit. Subjects will be instructed to return unused ibrutinib capsules dispensed during previous visits to the site. The theoretical number of ibrutinib capsules dispensed will be recorded and compared with the number returned and the drug accountability records will be updated by the study-site personnel at each visit.

During the study, the investigator or designated study-site personnel will be responsible for providing additional instruction to reeducate any subject who is not compliant with taking the study drug. Additional details may be provided in a pharmacy manual/study site investigational product and procedures manual that is provided separately and noted in Section 15, Study-specific Materials.

8. CONCOMITANT THERAPY

8.1. Permitted Concomitant Medications

8.1.1. Ancillary Therapy and Supportive Care

Ancillary therapy and supportive care for cGVHD is permitted as outlined in the NIH Consensus Development Project 2014 Ancillary Therapy and Supportive Care Working Group Report (Carpenter 2015, [Attachment 9](#)).⁷ In particular, the use of regimen to specifically treat or prevent bronchiolitis obliterans are allowed (eg, inhaled steroids/azithromycin/montelukast) and will not be considered systemic treatment for cGVHD.

Other supportive medications in accordance with standard clinical practice (such as for emesis, diarrhea, etc) are permitted. Use of neutrophil growth factors (filgrastim and pegfilgrastim) or red blood cell growth factors (erythropoietin) is permitted per institutional policy. Transfusions may be given in accordance with institutional policy.

8.1.2. Systemic Immunosuppressant Therapy

Participants may be receiving other immunosuppressive therapies in addition to glucocorticoids. In addition, due to potential drug-drug interactions with ibrutinib, monitoring of drug levels for immunosuppressant agents such as cyclosporine, tacrolimus, or sirolimus are highly recommended during the clinical trial. The doses for these immunosuppressants should be adjusted (increased or decreased) per institutional practices based on the measured drug level. Concurrent use of sirolimus and a CI (tacrolimus or cyclosporine) are prohibited.

Use of immunosuppressants for reasons other than treatment for cGVHD should be discussed with the medical monitor.

8.1.3. Systemic Steroids

Systemic corticosteroids may be decreased at the treating physician's discretion. The initial taper of corticosteroids may begin 2 weeks following initiation of ibrutinib if a clinical response is

seen. The recommendation is to not taper below 50% of the original dose by the 12-week assessment period unless there is a medical reason (eg, uncontrolled diabetes, infection) for steroid reduction below 50%. A specific steroid taper schedule will not be mandated.

By its nature, cGVHD is a protean disease with clinical manifestations that wax and wane over time. Closely spaced clinical evaluations will detect temporary exacerbations of cGVHD manifestations but may not accurately reflect the long-term trajectory of a subject's cGVHD and response to treatment. Therefore, in the event a participant experiences a flare of cGVHD, temporary reescalation of corticosteroids dose will be allowed at the physician's discretion. Tapering of increased corticosteroids dose for a flare will begin within 4 weeks. If criteria are met for progressive cGVHD, the participant will be scored as a treatment failure and dropped-off.

8.2. Prohibited Concomitant Medications

Any chemotherapy, anticancer immunotherapy, experimental therapy, or radiotherapy is prohibited while the subject is receiving ibrutinib treatment. Localized, hormonal, or bone sparing treatment for malignancies, and localized radiotherapy for medical conditions other than the underlying disease may be considered with prior approval of the medical monitor. The Sponsor must be notified in advance (or as soon as possible thereafter) of any instances in which prohibited therapies are administered.

8.3. Medications to be Used With Caution

8.3.1. CYP3A Inhibitors or Inducers

Ibrutinib is metabolized primarily by CYP3A4. Avoid coadministration with strong CYP3A inhibitors and consider alternative agents with less CYP3A inhibition. The dose of ibrutinib should be adjusted for concomitant use of CYP3A inhibitors as per [Table 7](#) below:

Table 7: Ibrutinib Dose Modifications for Concomitant Use of CYP3A Inhibitors

CYP inhibitor class	Dose modification instructions
Mild CYP3A inhibitors	420 mg once daily. No dose adjustment required.
Moderate CYP3A inhibitors	420 mg once daily. No dose adjustment required.
Voriconazole ^a	280 mg once daily
Strong CYP3A inhibitors	140 mg once daily or consider alternative with less CYP3A inhibitory potential

^a Itraconazole and ketoconazole will be replaced with voriconazole for study subjects. Avoid concomitant use of clarithromycin with ibrutinib.

When these antifungal agents will be discontinued, the ibrutinib dose will be increased to 420 mg, considering the half-lives of the antifungal agents. Avoid concomitant use of strong CYP3A inducers. Consider alternative agents with less CYP3A induction. Grapefruit and Seville oranges should be avoided during the study period. A list of common CYP3A inhibitors and inducers is provided in [Attachment 7](#). For further information, please refer to the current version of the ibrutinib IB and examples of inhibitors, inducers, and substrates may be found at

<http://medicine.iupui.edu/clinpharm/ddis/main-table/>. This website is continually revised and should be checked frequently for updates.

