4.2. Exclusion Criteria

Any potential subject who meets any of the following criteria will be excluded from participating in the study:

1. Active acute GVHD
2. More than 3 previous systemic treatments for cGVHD. Treatment with glucocorticoids is considered a treatment for cGVHD and should be included in determining the number of previous treatments.
3. History of treatment with a tyrosine kinase inhibitor (eg, imatinib), purine analogs, or other cancer chemotherapy in the 4 weeks prior to starting ibrutinib. Participants may have received ibrutinib pretransplant for other reasons besides cGVHD such as for the treatment of leukemia or lymphoma.
4. History of treatment with monoclonal T and B cell antibodies in the 8 weeks prior to starting ibrutinib.
5. Vaccinated with live, attenuated vaccines within 4 weeks of first dose of ibrutinib.
6. Received an investigational drug or used an invasive investigational medical device within 4 weeks before the first dose of ibrutinib.
7. Current treatment with sirolimus and either cyclosporine or tacrolimus
8. Requires treatment with a strong cytochrome P450 (CYP) 3A inhibitor ([Attachment 7](#)) with the exception of strong CYP3A inhibitors used for antifungal prophylaxis.
9. Concomitant use of warfarin or other Vitamin K antagonists.
10. More than 6 stools per day
11. Forced expiratory volume in 1 second (FEV1) <50% on pulmonary function tests.
12. Currently active, clinically significant cardiovascular disease, such as uncontrolled arrhythmia or Class III or IV congestive heart failure as defined by the New York Heart Association Functional Classification; or a history of myocardial infarction, unstable angina, or acute coronary syndrome within 6 months prior to the first dose of ibrutinib.
13. Uncontrolled active systemic infection or infection requiring systemic treatment that was completed \leq 7 days before the first dose of ibrutinib.
14. History of human immunodeficiency virus (HIV) or active with hepatitis C virus (HCV) or hepatitis B virus (HBV) infection. Subjects who are positive for hepatitis B core antibody, hepatitis B surface antibody (HBsAb), hepatitis B surface antigen (HBsAg), or hepatitis C antibody must have a negative polymerase chain reaction (PCR) result before enrollment.

Those who are PCR positive will be excluded.

15. Progressive underlying malignant disease including posttransplant lymphoproliferative disease (PTLD).

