6.1. Dose Modifications

6.1.1. Dose Modification for Adverse Reactions

The dose of ibrutinib must be modified according to the dose modification guidance in [Table 4](#) and [Table 5](#) if any of the following toxicities occur:

- Grade 4 neutropenia (ANC <500/ μ L) for more than 7 days
- Grade 3 thrombocytopenia (platelets <50,000/ μ L) in the presence of clinically significant bleeding events
- Grade 4 thrombocytopenia (platelets <25,000/ μ L)
- Grade 3 or 4 nausea, vomiting, or diarrhea if persistent, despite optimal antiemetic and/or antidiarrheal therapy
- Any other Grade 4 or unmanageable Grade 3 toxicity

Table 4: Ibrutinib Dose Modifications

Occurrence	Action
First	Withhold ibrutinib until recovery to Grade \leq 1 or baseline; may restart at original dose level
Second	Withhold ibrutinib until recovery to Grade \leq 1 or baseline; may restart at 1 dose level lower (ie, 280 mg/day for 420 mg/day dose)
Third	Withhold ibrutinib until recovery to Grade \leq 1 or baseline; may restart at 2 dose levels lower (ie, 140 mg/day for 420 mg/day dose)
Fourth	Discontinue ibrutinib

Table 5: Ibrutinib Dose Reduction Levels

Starting Dose Level	420 mg	280 mg	140 mg
Dose Reduction Level 1	280 mg	140 mg	70 mg
Dose Reduction Level 2	140 mg	70 mg	Discontinue
Dose Reduction Level 3	Discontinue	Discontinue	--

Refer to Section [8.3.1](#) for instructions on dose modifications or temporary hold during concomitant administration of CYP3A inhibitors or inducers and Section [8.3.3](#) for subjects requiring the initiation of anticoagulants while receiving ibrutinib. Refer to Section [4.3](#) for

guidance on dose delays during the perioperative period for subjects who require surgical intervention or an invasive procedure while receiving ibrutinib.

For Grade 3 or 4 atrial fibrillation or persistent atrial fibrillation of any grade, consider the risks and benefits of ibrutinib treatment. If clinically indicated, the use of anticoagulants or antiplatelet agents may be considered for the thromboprophylaxis of atrial fibrillation.

Study drug may be held for a maximum of 28 consecutive days. Discontinue ibrutinib permanently if ibrutinib cannot be restarted within 28 days due to toxicity. If the dose of ibrutinib is reduced for a toxicity, at the investigator's discretion, the dose of ibrutinib may be reescalated after 8 weeks of a dose reduction in the absence of a recurrence of the toxicity that led to the reduction.

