6.1.2. Dose Modification for Subjects with Hepatic Impairment

Dose modifications for hepatic impairment will depend on baseline total bilirubin level and subsequent changes in bilirubin levels per [Table 6](#) below. If the elevation of bilirubin is due to a nonhepatic cause or Gilbert's Syndrome then no dose modifications are necessary.

Table 6: Ibrutinib Dose Modifications for Subjects with Hepatic Impairment

Starting Dose Level	Bili $\leq 1.5 \times$ ULN at baseline: 420 mg
On-study bilirubin level $\leq 1.5 \times$ ULN	Continue 420 mg
On-study bilirubin level $> 1.5-3 \times$ ULN	Reduce to 140 mg
On-study bilirubin level $> 3 \times$ ULN	Hold* until bili level $> 1.5-3 \times$ ULN restart at 140 mg When bili level $\leq 1.5 \times$ ULN restart at 420 mg

Bili = bilirubin; ULN = upper limit of normal

* In cases where the investigator wishes to restart ibrutinib after ibrutinib has been held for more than 28 days for hepatic impairment, please contact the medical monitor for approval.

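### Section 8.3.1 returns ibrutinib to a fixed 420 mg when the antifungal stops, with no exception for a toxicity or bilirubin reduction still in force

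*Protocol*

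**What the plan says.** Three sets of dose rules can apply to the same subject.

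- **CYP3A inhibitors (Protocol 8.3.1, Table 7).** The dose is 280 mg with voriconazole. For other strong inhibitors the entry is "140 mg once daily or consider alternative with less CYP3A inhibitory potential". When the antifungal stops: "When these antifungal agents will be discontinued, the ibrutinib dose will be increased to 420 mg, considering the half-lives of the antifungal agents".
- **Toxicity (Protocol 6.1.1, Tables 4 and 5).** Modification is mandatory for the listed toxicities. A second occurrence costs one dose level. After a third, the subject "may restart at 2 dose levels lower (ie, 140 mg/day for 420 mg/day dose"). Upward movement is left to the investigator: "the dose of ibrutinib may be reescalated after 8 weeks of a dose reduction in the absence of a recurrence of the toxicity".
- **Bilirubin (Protocol 6.1.2, Table 6).** For a subject who started at 420 mg, the instruction at >1.5-3 × ULN is "Reduce to 140 mg". After a hold, once bilirubin is ≤1.5 × ULN, it is "ULN restart at 420 mg".

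Section 6.1.1 refers the reader to 8.3.1 "for instructions on dose modifications or temporary hold during concomitant administration of CYP3A inhibitors or inducers". Section 8.3.1 does not refer back to 6.1. Exclusion criterion 8 bars subjects who need a strong inhibitor, "with the exception of strong CYP3A inhibitors used for antifungal prophylaxis", and Section 6 expects many subjects to need such prophylaxis.

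**The concern.** The sentence in 8.3.1 names a fixed dose and is worded as a directive. It is right for a subject whose only reduction came from Table 7. For a subject with a second reason to be on a lower dose, it conflicts with the rule that set that dose.

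The overlap is foreseeable. Table 5 has starting columns for 280 mg and 140 mg, the two doses that Table 7 produces, so the protocol provides for a toxicity reduction in a subject already on an inhibitor-adjusted dose. The way down is specified, but the way back up ignores it. The 8-week condition is also deliberate: the Amendment 1 log says it was introduced to match the earlier cGVHD study.

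At stake is a safety reduction cancelled before its own condition for re-escalation is met, and different dosing at different sites for the same situation.

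**Working it through.** The plan gives no figure on this point to reproduce. The check is a comparison of rules followed by dose ratios.

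**Step 1: does any text rank the rules?**

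- Section 6 and Attachment 7 direct the reader to the relevant sections without saying which prevails.
- The cross-reference in 6.1.1 concerns the period of inhibitor use, not its end.
- The medical-monitor consultation in 6.1.1 is for toxicities outside the listed ones. The monitor approval in 6.1.2 is for hepatic holds beyond 28 days.
- Sections 3.1 and 9.1.3 say that dosing is modified under Section 6.1 during treatment, but do not mention 8.3.1.

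No order of precedence is stated.

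**Step 2: size of the excess.** Part of the rise on stopping an antifungal is proper, because it reverses Table 7. The comparison is therefore with the dose the remaining rule allows when no inhibitor is present: the same reduction level in Table 5's 420 mg column (420 → 280 → 140), or Table 6's 140 mg.

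Excess = 420 ÷ dose allowed by the remaining rule.

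| Situation when the antifungal stops | Dose being taken | Dose the remaining rule allows | Excess at 420 mg |
|---|---|---|---|
| Voriconazole (280 mg start), toxicity level 1 | 140 mg | 280 mg | 420/280 = 1.5 |
| Voriconazole (280 mg start), toxicity level 2 | 70 mg | 140 mg | 420/140 = 3 |
| Other strong inhibitor (140 mg start), toxicity level 1 | 70 mg | 280 mg | 420/280 = 1.5 |
| 420 mg start, bilirubin >1.5-3 × ULN | 140 mg | 140 mg | 420/140 = 3 |

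For a 140 mg start at level 2, Table 5 says to discontinue, so that case does not arise. Under Table 4, level 1 needs a second occurrence and level 2 a third.

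The nominal rises are larger. In the first row, 420/140 = 3, of which 280/140 = 2 is the correct reversal of Table 7 and 3/2 = 1.5 is the excess.

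**Step 3: Table 6 restart.** Take a subject who started at 420 mg, was reduced for toxicity, and was then held for bilirubin. Restarting at 420 mg gives 420/280 = 1.5 times the level 1 dose or 420/140 = 3 times the level 2 dose. No inhibitor is needed for this. If an inhibitor was started in the meantime, the same ratios arise against Table 7 (280 mg for voriconazole, 140 mg for another strong inhibitor).

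**The case against.** The strongest reply is that each table handles one factor and should be read that way. Taken in isolation, Table 6's first row (stay at 420 mg with acceptable bilirubin) and Table 7's entry for moderate inhibitors (420 mg) would each cancel every toxicity reduction, and no site would read them so. The 8.3.1 sentence sits directly under Table 7 and most naturally reverses only Table 7. Section 6.1.1 is mandatory, and Sections 3.1 and 9.1.3 keep Section 6.1 in force throughout treatment. Table 6's 140 mg is itself a standing rule for as long as bilirubin stays in its band.

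Much of this stands. It makes the misreading less likely, and many sites would dose correctly. The bilirubin part is weakened, as is the case of an inhibitor started before a Table 6 restart: Table 7 is also a standing rule, and SAP 2.9 treats 420 mg as a default that inhibitor use displaces. But the reply does not remove the conflict. The 8.3.1 sentence is an instruction to raise the dose to a stated value at a stated event, and a site that follows it gives the wrong dose.

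The earlier cGVHD study (Protocol 1.4.2) found no association of inhibitor use with dose reductions or discontinuations. That is reassuring in general, but it did not test stopping an inhibitor while a reduction is in force.

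**Conclusion.** The point holds as a minor dosing-safety correction. The excess is 1.5 times at toxicity level 1, 3 times at level 2, and 3 times while bilirubin is >1.5-3 × ULN. The Table 6 restart is a lesser, parallel gap, clearest against an earlier toxicity reduction. All of this assumes that the sentence is followed literally. No harm is shown, and the endpoint, sample size and power are unaffected.

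A reader might infer three stronger things that the documents do not support.

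- *That any subject held at 140 mg is overdosed three-fold.* A voriconazole subject cut one level for toxicity should go to 280 mg, so the excess is 1.5 times.
- *That the number affected can be bounded.* In the earlier study 14.3% of 42 (6) took voriconazole and 9.5% (4) posaconazole. Scaling to 17 gives 6/42 × 17 = 2.4 with full overlap to 10/42 × 17 = 4.0 with none. This is not an upper limit: use here may differ, and 8.3.1 moves itraconazole and ketoconazole users to voriconazole. Nor is it an estimate, because a reduction must also be in force when the antifungal stops, and no rate is given for that. Few subjects is a judgement based on the need for both events.
- *That the 8.2-fold higher AUC in Child-Pugh B (Protocol 1.4.2) applies to the bilirubin case.* Table 6's band is bilirubin alone, in multiples of ULN. Child-Pugh class uses five measures; bilirubin of 2-3 mg/dL with the other four at one point scores 2 + 4 = 6, class A. The earlier cGVHD study found no exposure difference with mild hepatic impairment.

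**What to change.** In Section 8.3.1, replace the return to 420 mg with wording such as: *the dose is returned to the dose that would apply without the inhibitor. This is 420 mg; or, if a toxicity reduction is in force, the same reduction level in the 420 mg column of Table 5; or, if a bilirubin reduction is in force, the Table 6 dose; or the lower of the two if both are in force. Any such reduction is lifted only under Section 6.1.1 or 6.1.2.* The allowance for the antifungal's half-life stays.

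In Table 6, replace the restart at 420 mg with: *restart at the dose otherwise applicable under Tables 5 and 7.*

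A general rule of taking the lowest dose allowed by any table looks simpler but should not be used, because it does not stack reductions. A subject at 280 mg for toxicity who then starts voriconazole would get min(280, 280) = 280 mg, although Table 5's 280 mg column steps down to 140 mg.

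The cost is amendment wording and slightly lower dosing in a few subjects; the documents do not allow any loss of efficacy from that to be estimated. Sample size, visits and analyses do not change.

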8.3.2. Substrates of P-glycoprotein

In vitro studies indicated that ibrutinib is not a substrate of P-glycoprotein (P-gp), but is a mild inhibitor. Ibrutinib is not expected to have systemic drug-drug interactions with P-gp substrates.

However, it cannot be excluded that ibrutinib could inhibit intestinal P-gp after a therapeutic dose. There is no clinical data available. Therefore, to avoid a potential interaction in the GI tract, narrow therapeutic range P-gp substrates such as digoxin, should be taken at least 6 hours before or after ibrutinib.

8.3.3. Antiplatelet Agents and Anticoagulants

Warfarin or other vitamin K antagonists should not be administered concomitantly with ibrutinib. Supplements such as fish oil and vitamin E preparations should be avoided. Use ibrutinib with caution in subjects requiring other anticoagulants or medications that inhibit platelet function. Subjects with congenital bleeding diathesis have not been studied. Ibrutinib should be withheld at least 3 to 7 days pre and postsurgery depending upon the type of surgery and the risk of bleeding (see Section 4.3).

For subjects requiring the initiation of therapeutic anticoagulation therapy (eg, atrial fibrillation), (other than warfarin or a vitamin K antagonist) the risks and benefits of continuing ibrutinib treatment should be considered. If therapeutic anticoagulation is clinically indicated during the course of the study, treatment with ibrutinib should be held and ibrutinib should not be restarted until the subject is clinically stable and has no signs of bleeding. Subjects should be observed closely for signs and symptoms of bleeding. No dose reduction is required when ibrutinib is restarted.

9. STUDY EVALUATIONS

9.1. Study Procedures

9.1.1. Overview

The **TIME AND EVENTS SCHEDULE** summarizes the frequency and timing of efficacy, PK, PD, and safety assessments applicable to this study. The study visits scheduled should occur at the times delineated in the **TIME AND EVENTS SCHEDULE**. The Week 1 and Week 2 visits should occur on the specified day and visits from Week 5 and onwards that are to occur every 4th week should occur within ± 3 days of the scheduled visit date. Visits from Week 37 and onwards that are to occur every 12th week and all the other study visits in the treatment period should occur within ± 7 days of the scheduled visit date. The End-of-treatment visit is scheduled after 30 days from last dose of ibrutinib. Posttreatment follow-up visit will occur every 12th week after End-of-treatment visit, until cGVHD progression. After cGVHD progression, survival status and the use of subsequent cGVHD treatment will be followed every 12th week by clinic visits or telephone contacts.

Lee cGVHD Symptom Scale assessment (whenever assessment is scheduled) should be conducted/completed before any tests, procedures, or other consultations to prevent influencing subject perceptions. Blood collections for PK and PD assessments should be kept as close to the specified time as possible. Actual dates and times (if applicable), of assessments will be recorded in the source documentation and case report form (CRF).

Additional serum or urine pregnancy tests may be performed, as determined necessary by the investigator, to establish the absence of pregnancy at any time during the subject's participation in the study.

The total blood volume to be collected from each subject will be approximately 319.5 mL in the first year [from screening to Week 49], 135 mL per year after the first year [5 times visits per year], and 27 mL on the End of Treatment Visit. If a subject continues treatment phase until Week 109, the total blood volume is approximately 481.5 mL (255 mL for safety [85 mL for hematology and 170 mL for serum chemistry], 5 mL for coagulation studies, 3 mL for serology, 2 mL for serum β -hCG pregnancy test [women only], 77 mL for donor/host chimerism, 55 mL for quantitative serum immunoglobulins [Igs], 22 mL for PK, and 62.5 mL for PD). Repeat or unscheduled samples may be taken for safety reasons or for technical issues with the samples.

